3.6 Analysis plan

3.6.1 Drug utilization patterns

Based on the dates of rosiglitazone marketing, publications, and regulatory decisions, the following four broad periods can be identified, in which drug utilization patterns will be examined, starting with 1 July 2000, when rosiglitazone was introduced to the EU market:

- | | |
|----------|---|
| Period 1 | 1 July 2000 to 23 May 2007 (meta-analysis & by EMA's press release) |
| Period 2 | 24 May 2007 to 24 January 2008 (EMA adds contra-indications) |
| Period 3 | 25 January 2008 to 22 September 2010 (EMA suspends rosiglitazone) |
| Period 4 | 23 September 2010 until data closing date. |

We will evaluate prescribing patterns within these periods and according to calendar month by several methods. First, we will calculate (separately in Denmark and in the UK):

- The number of persons receiving prescriptions for rosiglitazone in each time period, overall and per month during the time period;
- The number of prescriptions for rosiglitazone in each time period, overall and per month during the time period;
- The number of persons receiving a prescription for any specific antidiabetic medication in each time period, overall and per month during the time period;

- The proportion of persons receiving a prescription for any specific antidiabetic medication who received a prescription for rosiglitazone in each time period.

We will describe switching patterns in several ways within each database. First we will determine the proportion of patients on anti-diabetic therapies other than rosiglitazone who switched to rosiglitazone in each of the 4 time periods. We will also describe the proportion of people, by time period, who switched from rosiglitazone to another anti-diabetic medication or who discontinued use of any anti-diabetic medication. Proportions of patients discontinuing rosiglitazone preparations will be determined among those who originally switched to rosiglitazone and among those for whom the rosiglitazone-containing product was the first-ever anti-diabetic prescription. Switching will be defined as 1) stopping all rosiglitazone prescriptions and starting a different anti-diabetic medication, 2) stopping all anti-diabetic medications or 3) adding new anti-diabetic therapies to the current rosiglitazone therapy (concomitant therapies). A person will be considered a switcher once they have received at least 2 prescriptions for a new therapy.

To more clearly display time trends and the influence of the milestones that separate the time periods, we will create smoothed plots of the four parameters listed in the bullets above. We will define a window of length four months, and calculate each of the four parameters in that window, beginning in the first four months of 2000 (January, February, March, and April). We will plot the values of the four parameters at the midpoint of the window (1 March 2000). We will then slide the window one month forward and recalculate all four parameters in that window (February, March, April, and May of 2000). Data from January of 2000 falls out of the window and data from May of 2000 enters the window). We will plot the values of the four points at the midpoint of the window (1 April 2000). We will continue to slide the four-month window along the time axis until the end of the study period, calculating the parameters and plotting them at the midpoint of each window. The result will be a smoothed plot of trends in the parameters. We expect, for example, that the number of prescriptions for rosiglitazone will not exceed 0 until the first window that includes August 2000 appears. The number of prescriptions for rosiglitazone will likely increase, then reach a steady state, then decrease with the first milestone (May 2007). We will depict these milestone events on the graph, which will clearly display the correspondence between changes in the parameters and the milestone events.

This method of smoothing the results depicts trends without imposing a model on the data. A model embeds assumptions, such as the expected changes in trends at the milestones, which can become a self-fulfilling prophecy. It is important to begin the analysis without a model. If the smoothed data suggest that models of these results would be productive, and the modelling results would be useful, then we will fit models of the appropriate form. We expect these models will require regression splines, with knots (nodes) at the milestone dates. Such models would allow us to calculate, for example, the rate of change in number of prescriptions or proportion of diabetics receiving prescriptions within time periods. The model would also allow a quantitative comparison of the change in proportion in Denmark versus the UK, as a measure of homogeneity of the response in Europe to the milestone events.

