Concerns have been raised about cardiovascular safety of rosiglitazone, based on the initial (2007) and the updated (2010) meta-analyses of clinical trials by Nissen and Wolski^{3,4} and a Medicare-based study by Graham et al.⁵ These studies provided evidence of an increased risk of several cardiovascular outcomes in users of rosiglitazone compared with users of other oral antidiabetic medications or placebo. The postmarketing RECORD trial, ordered by a regulator and sponsored by the manufacturer, GlaxoSmithKlein, published in 2010,⁶ showed no overall effect of rosiglitazone on the primary outcome of cardiovascular morbidity and mortality. The trial, however, has been criticized for methodological flaws, including open-label design, considerable selection bias, and possible irregularities in case adjudication.⁷

In response to the safety concerns raised in 2007, EMA emphasised the need for providers "to adhere to the restrictions for use in patients with cardiac disease", but advised patients "not to stop treatment with rosiglitazone and to discuss the medication with their doctor at their next regular visit."⁸ In 2007, EMA concluded "that the benefits of [...] rosiglitazone [...] in the treatment of type 2 diabetes continue to outweigh their risks."⁹ In January 2008, EMA added contraindications for rosiglitazone to its label.¹⁰ The Food and Drug Administration in the United States also issued a boxed warning. The proportion of rosiglitazone prescriptions among all diabetic medications except insulin dropped in the US from around 11% in March 2007 to 6% in July 2007 and to less than 3% in 2009.¹¹

Following the two 2010 publications,^{4,5} the EMA suspended rosiglitazone-containing drugs from the European markets, on 23 September 2010.¹² On 3 December 2010, the European Commission (EC) issued a suspension decision, noting that risk minimisation in form of label warnings and restricted use has not been clearly effective. The scientific discussion accompanying the suspension decision noted that persons with indications for rosiglitazone may have an a-priori higher risk of cardiovascular morbidity. Still, based on all available evidence, the EC concluded that rosiglitazone does not provide unique therapeutic benefits that outweigh the risks of cardiovascular outcomes.¹³

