3.6.2 Contraindications for use and off-label use

Prevalence of contraindicated or off-label use will be examined according to calendar time, where events marking relevant scientific publications and regulatory decisions will be marked. We will

report the number and proportion of patients prescribed rosiglitazone who had a diagnosis consistent with a contraindication for rosiglitazone use or with off-label use as defined in the Methods. We will provide the proportions in each country and over time. We will follow the analytic methods described above, provided that the sample size is large enough. At a minimum, use by patients with the additional contraindications (ischemic heart disease and/or peripheral vascular disease) listed in the 2008 press release¹⁰ will be examined in the periods before and after the publication of the press release including any prior diagnosis of liver disease, ischemic heart disease, cardiac failure, or acute coronary syndrome.

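### The plotted rosiglitazone series and the contraindicated and off-label proportions mix first-time with continuing users, so a prompt change in who is started shows only as a gradual drift

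*Protocol*

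**What the plan says.** Section 3.6.1 lists four utilisation parameters. Three concern rosiglitazone directly:

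- persons: "The number of persons receiving prescriptions for rosiglitazone in each time period, overall and per month during the time period";
- prescriptions: "The number of prescriptions for rosiglitazone in each time period, overall and per month during the time period";
- the proportion of antidiabetic users "who received a prescription for rosiglitazone in each time period".

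The remaining one counts persons on any specific antidiabetic drug. None distinguishes a first from a repeat prescription. These four are what is drawn against the milestones: "we will create smoothed plots of the four parameters listed in the bullets above".

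The same section also plans measures of flow, by broad period only: "the proportion of patients on anti-diabetic therapies other than rosiglitazone who switched to rosiglitazone in each of the 4 time periods" and, separately, "the proportion of people, by time period, who switched from rosiglitazone to another anti-diabetic medication or who discontinued use of any anti-diabetic medication".

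For contraindications and off-label use, section 3.6.2 will "report the number and proportion of patients prescribed rosiglitazone who had a diagnosis consistent with a contraindication for rosiglitazone use", or with off-label use, by country and over time. At a minimum it compares the periods before and after the 2008 press release. Section 3.4.1 takes the contraindicating conditions from diagnoses dated before the first rosiglitazone prescription.

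The background text reports that in 2007 the regulator asked providers to keep to the cardiac restrictions and advised patients "not to stop treatment with rosiglitazone and to discuss the medication with their doctor at their next regular visit".

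**The concern.** The first aim in section 2 is to describe how utilisation responded to external events. Two groups can respond: prescribers deciding whom to start, and patients and prescribers deciding whether to continue. The 2007 advice told current users not to stop, so continued use in Period 2 is not in itself a failed response. Yet continuing users are part of every rosiglitazone series on the plots.

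The issue is sharper in section 3.6.2. A patient with ischaemic heart disease who started in 2005 is counted as contraindicated for as long as prescriptions continue, and one without such a history is never counted. The all-user proportion can move only as people enter or leave. After January 2008 it blends people started under the new contraindications with people started before those contraindications existed. A reader of the before/after comparison cannot tell whether a residual proportion reflects new contraindicated starts or older patients who remain on treatment, and these are different findings about risk minimisation.

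The spline models foreseen in section 3.6.1 would compare Denmark with the UK as a measure of homogeneity of response. With all-user series, identical behaviour at initiation would look different if turnover differed between the countries.

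**Working it through.** The protocol states no figure on this point, so there is nothing to reproduce. What follows is an illustrative stock-and-flow calculation.

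**Inputs from the protocol (section 3.6.1).** Period 2, 24 May 2007 to 24 January 2008: 246 days, about 8.1 months. Period 3, 25 January 2008 to 22 September 2010: 972 days, about 31.9 months.

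**Assumptions, not in the protocol.** Before the milestone the pool of users is steady, with monthly starts and monthly stops both equal to a fraction f of the pool, f = 1% to 5%. The contraindicated share before the milestone is c = 20%, with 10% and 30% as alternatives. From the milestone no contraindicated patient is started; other starts and all stops are unchanged.

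**Share in the month, t months after the milestone.** Contraindicated users decay to c(1−f)^t, while the others stay at 1−c:

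share = c(1−f)^t / [c(1−f)^t + (1−c)]

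For c = 0.20, t = 8, f = 0.01: 0.99^8 = 0.923, so 0.1845/0.9845 = 18.7%. For f = 0.05: 0.95^8 = 0.663, so 0.1327/0.9327 = 14.2%.

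**Share among everyone prescribed during the 32 months of Period 3.** All users at the outset count, plus the non-contraindicated starters:

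share = c / [c + (1−c)(1+32f)]

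For f = 0.01: 0.20/(0.20 + 0.80×1.32) = 15.9%. For f = 0.05: 0.20/(0.20 + 0.80×2.60) = 8.8%.

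| Monthly turnover f | All-user share, month 8 | Share of all prescribed in Period 3 | Share among starters |
|---|---|---|---|
| 1% | 18.7% | 15.9% | 0% |
| 2% | 17.5% | 13.2% | 0% |
| 3% | 16.4% | 11.3% | 0% |
| 5% | 14.2% | 8.8% | 0% |

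With a 10% prior share the month-8 figures run from 9.3% to 6.9%; with 30%, from 28.3% to 22.1%. The dilution fades late at high turnover: with f = 5% and c = 20% the monthly share is 4.6% by month 32.

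**Utilisation counts.** If starts are halved and the stop rate h is unchanged, the pool after 8 months is 0.5 + 0.5(1−h)^8 of its former size. For h = 0.02 this is 0.925, a 7.5% fall; for h = 0.05 it is 0.832, a 16.8% fall. Starts themselves have fallen by 50%.

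**Coverage of the planned start measure.** The switch-to proportion has patients already on other therapies as its denominator, so first-line rosiglitazone starters have no place in it. The written definition of switching in section 3.6.1 lists leaving rosiglitazone, stopping all therapy, or adding to rosiglitazone. It does not describe moving to rosiglitazone or adding it to something else, although the rule of two prescriptions for a new therapy might be read to include these. Section 3.3 names first-line, switch and add-on starters as categories, but section 3.6.1 does not count all starts by month or period, and section 3.6.2 gives no contraindicated share among starters.

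**The case against.** The strongest reply is that the all-user measures fit the aims. Section 2 asks for trends in utilisation and for the extent of use in persons with potential contraindications, and extent includes continuing users. After January 2008, continued use by someone with a newly listed contraindication is a result in its own right. The 2007 advice also sent patients to discuss the drug with their doctor, so it was not directed only at starts. All of this stands, and it is why the all-user series should be kept.

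Secondly, a reader might infer that the plan cannot tell stopping from not starting. The protocol does not support that. Section 3.6.1 reports switching to rosiglitazone, and separately switching from it or discontinuing, by period, and splits discontinuation by whether rosiglitazone was the first-ever therapy. The gap is confined to the plotted series and to section 3.6.2.

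Thirdly, all-user figures may move quickly if stopping rises. The background text gives the US rosiglitazone share of non-insulin prescriptions as about 11% in March 2007 and 6% in July 2007, a relative fall of about 45%. That is another country, but it shows that the constant stop rate assumed above need not hold. The sliding windows and the possible splines could also show a change of slope where the level moves slowly. Neither would say whether the change came from starts or stops.

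Finally, stratification is often left to a statistical analysis plan. Here, however, the protocol itself fixes the plotted parameters and the denominator for contraindicated use.

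**Conclusion.** The point holds for the plotted rosiglitazone series and for the proportions in section 3.6.2. Under the stated assumptions, complete cessation of contraindicated starts would leave a 20% all-user share at about 14–19% after 8 months, and at about 9–16% of all persons prescribed in Period 3, while the share among starters is 0%.

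These sizes rest on assumed turnover, an assumed prior share and a constant stop rate. Two further readings go beyond the documents. One is that most users after January 2008 had started earlier: with 2–5% monthly stopping and later starts at 25–100% of replacement, new users make up 32hk/(1+32hk) of Period 3 users (h the stop rate, k the replacement fraction), so earlier starters are anywhere from 38% to 86%. The other is that full compliance at initiation must look like a weak response: at 5% turnover the fall from 20% to 8.8% is substantial.

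The argument about fixed status applies to contraindications. Off-label status in section 3.4.2 is partly set during use, through age at any rosiglitazone prescription and insulin between the first and last ones. Those proportions still mix starters with continuing users, but a continuing user's status is not always settled at the start.

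This should be changed, because it determines what the January 2008 comparison can conclude.

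**What to change.** Keep the all-user series. Derive one flag for the first-ever rosiglitazone prescription, labelled first-line, switch or add-on. Report each rosiglitazone series in section 3.6.1 and each proportion in section 3.6.2 separately for initiators (flag in that month or period) and continuing users (an earlier rosiglitazone prescription), by month and by period, and plot both against the milestones. Give the before/after January 2008 comparison for both groups. State in section 3.6.1 how a move to rosiglitazone, and its addition to another therapy, are classified.

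The cost is one derived variable and an extra line per plot; the prescription dates and patient identifiers are already held (section 3.3).

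The main drawback is sparse monthly counts in Denmark. About 2,400 users over Periods 1 to 3 (2,518 + 246 + 972 = 3,736 days, or 122.7 months) average 2,400/122.7 ≈ 20 initiators a month if starts were evenly spread, of whom about 4 would be contraindicated at an assumed 20%. The planned four-month window raises these to about 78 and 16, and period totals can be used where that is still too few. The UK database, with about 20,000 users, would average about 163 a month.

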In the UK, the study will be conducted based on data from the General Practice Research Database (GPRD). The GPRD is an ongoing longitudinal database that collects data from over 350 general practices in the UK since 1987. The UK provides a unique medical environment to create a computerized medical data resource for medical epidemiological research for two main reasons: a) the primary health care system comprehensively covers the UK population; b) the information on all relevant medical care is located in the offices of the general practitioners (GPs), who function as "gatekeepers" for hospital and specialist referrals in the UK health system. The GPRD contains information on more than 6 million patients, of whom 3.5 million are currently registered, and a

cumulative follow-up time of more than 40 million person-years. It covers 6% of the UK population; this sample is representative with respect to age, gender and race/ethnicity distribution.

The study population will include, in both countries, diabetic patients treated with oral glucose lowering drugs between 1 January 2000 and 1 January 2011. This period covers the time from the approval of rosiglitazone for use in the European Union, in July 2000, until the decision by the European Medicines Agency to suspend the drug, on 23 September 2010. The study period also includes a pre-approval and a post-suspension periods to allow examination of drug utilization patterns in response to these events.

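### Three of the four utilisation measures are raw counts; if the UK database grew during the study, its count curves may understate falls in rosiglitazone use after 2007

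*Protocol*

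**What the plan says.** Protocol section 3.6.1 lists four measures, calculated separately in each country:

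1. "The number of persons receiving prescriptions for rosiglitazone in each time period, overall and per month during the time period"
2. "The number of prescriptions for rosiglitazone in each time period, overall and per month during the time period"
3. "The number of persons receiving a prescription for any specific antidiabetic medication in each time period, overall and per month during the time period"
4. "The proportion of persons receiving a prescription for any specific antidiabetic medication who received a prescription for rosiglitazone in each time period"

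The first three are counts; only the fourth has a denominator. For the smoothed plots, the plan will "calculate each of the four parameters in that window", moving a four-month window forward one month at a time and marking the milestones on the graph. The response expected at May 2007 is described on the number of rosiglitazone prescriptions. If models are fitted later, an example of their output is "the rate of change in number of prescriptions or proportion of diabetics receiving prescriptions within time periods". The quantitative comparison between Denmark and the UK is framed on the change in the proportion.

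Section 3.1 says that the UK database has collected data since 1987. It holds more than 6 million patients, "of whom 3.5 million are currently registered", with a "cumulative follow-up time of more than 40 million person-years". No yearly registered population is given, and the protocol does not discuss whether the size of the UK source population changes over the study.

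**The concern.** In the UK, a prescription is seen only while the patient is registered with a contributing practice. A monthly count is therefore the product of prescribing per registered person and the number of persons registered. If the second factor rises, the count falls by less than prescribing does.

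Aim 1 is to describe how utilisation responded to the external events. Three of the four curves used for this cannot separate prescribing from database size. Prescription volume is the most exposed: it is the series on which the expected May 2007 response is stated, and the plan gives it no denominator. The protocol's own UK figures make a constant base doubtful.

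**Working it through.** **Inputs from the protocol.** UK data since 1987; 3.5 million registered currently; more than 40 million person-years (section 3.1). Period 2 starts on 24 May 2007 (2007.39). Period 3 runs from 25 January 2008 to 22 September 2010, midpoint about 2009.39 (section 3.6.1).

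**Assumptions, not in the protocol.** The date meant by currently (2010 to the start of 2011), the shape of growth, and how far the total exceeds 40 million.

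**Is a constant base compatible with the stated total?**

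- Constant 3.5 million for 23-24 years: 3.5 × 23 = 80.5 to 3.5 × 24 = 84.0 million person-years, about twice 40 million.
- Average size at 40 million: 40/24 = 1.67 to 40/23 = 1.74 million, about half the current size.

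A total near 40 million therefore means that the database grew at some time after 1987.

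**Must the growth fall within 2000-2010?** A flat 3.5 million over the 11 study years uses 3.5 × 11 = 38.5 million. What remains for the 13 years 1987-2000 is:

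- total 40 million: 1.5/13 = 0.12 million registered on average;
- total 50 million: 11.5/13 = 0.88 million;
- total 60 million: 21.5/13 = 1.65 million.

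At 40 million, no growth during the study is arithmetically possible but requires an almost empty database before 2000. At 50 or 60 million it is an ordinary path.

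**How much masking if growth was linear from 2000 to 3.5 million at the start of 2011?** Let P0 be the registered population (millions) in 2000 and PY the total person-years (millions). Person-years in 2000-2011 are 5.5 × (P0 + 3.5). Person-years in 1987-2000 are 6.5 × P0 if the database rose linearly from zero, or 13 × P0 if it was flat.

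- Rise from zero: P0 = (PY − 19.25)/12
- Flat: P0 = (PY − 19.25)/18.5
- Size at time t: N(t) = P0 + (3.5 − P0)(t − 2000)/11
- Growth factor: g = N(2009.39)/N(2007.39)
- Apparent fall in the count for a true 40% per-capita fall: 1 − 0.6g

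| Total PY | Before 2000 | P0 | N, May 2007 | N, mid-Period 3 | g | Apparent fall |
|---|---|---|---|---|---|---|
| 40 | rise from zero | 1.73 | 2.92 | 3.24 | 1.11 | 33% |
| 40 | flat | 1.12 | 2.72 | 3.15 | 1.16 | 30% |
| 50 | rise from zero | 2.56 | 3.19 | 3.36 | 1.05 | 37% |
| 50 | flat | 1.66 | 2.90 | 3.23 | 1.12 | 33% |
| any | no growth after 2000 | 3.50 | 3.50 | 3.50 | 1.00 | 40% |

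On the two 40 million paths the base grows by about 0.16-0.22 million a year, or 5.5-8% of its May 2007 size. That is roughly 2-3% per four-month window.

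**The case against.** The strongest reply is that the denominator already exists where it matters. The fourth measure is a proportion, is recalculated in every sliding window, and is the basis of the only quantitative country comparison described. Changes in database size largely cancel in it, so a real fall in the share of treated patients receiving rosiglitazone would still show. Switching and discontinuation are also planned as proportions by period. All of this stands, and it rules out the reading that a UK fall is hidden from the study or that the Denmark-UK comparison is invalid. It does not supply a denominator for prescription volume, and it does not give use per registered population.

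Second, 40 million is a lower bound and no yearly series is given, so a reader who concludes that the UK population must have grown during the study goes further than the figures allow. This stands too; growth is probable only if the total is near 40 million.

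Third, a reader might compare whole-period means. On the 40 million paths above, the mean registered population in Period 3 is 37-60% higher than in Period 1, and a true 40% fall would shrink to 4-18%. That contrast is not the one the plan uses to read milestones. Period 1 runs back to market launch and includes the uptake from zero, whereas the plots are read locally. The relevant growth is the 11-16% from May 2007 to mid-Period 3.

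Fourth, a reader might infer that late-arriving practice data will imitate a fall after the suspension. The protocol does not say that any records are missing at that point, so this is a reason for care in defining person-time and not a demonstrated bias.

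Finally, details of any model could be left to a statistical analysis plan. The three count measures, however, are fixed in the protocol itself.

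**Conclusion.** The point holds as a possible, moderate bias in three of the four UK curves. If the total is near 40 million person-years and growth was linear from 2000, a true 40% per-capita fall from May 2007 to mid-Period 3 would show as about 30-33% in the counts. At 50 million it would show as about 33-37%, and with all growth before 2000 there would be no masking. The result rests on the assumed growth path and on the distance of the true total from 40 million, neither of which the protocol fixes. The proportion of treated persons receiving rosiglitazone and the comparison of proportions between countries are largely unaffected. This is a low-cost improvement that makes the count curves interpretable; it does not overturn the utilisation analysis.

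**What to change.** For each month, period and sliding window, report the first three measures also per 1,000 registered person-months:

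- **UK:** person-time from the registration, departure and death dates in the Registration File (section 6.2), counted only while a practice's data are being received. The protocol does not list a last-collection date per practice, so its availability should be confirmed.
- **Denmark:** residents of the two regions, from the Central Personal Registry (section 6.1) if region of residence by date is available, otherwise the published size of the regional population.

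Report rosiglitazone prescriptions also per 1,000 persons treated with glucose-lowering drugs. If a spline is fitted to prescription numbers, include person-time as an offset. Keep the raw counts alongside the rates.

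The cost is a modest amount of extra programming, mostly on dates already held. Nothing now planned is lost.

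### Switching and stopping are reported as raw proportions over periods of very unequal length, with no person-time, so a real rise after a warning could appear as a fall

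*Protocol*

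**What the plan says.** Protocol section 3.6.1 divides calendar time at the regulatory milestones: Period 1, "1 July 2000 to 23 May 2007"; Period 2, "24 May 2007 to 24 January 2008"; Period 3, "25 January 2008 to 22 September 2010"; and Period 4, "23 September 2010 until data closing date".

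Four utilisation measures are listed as bullets. The first three, which are counts of persons or prescriptions, are to be given for each period and also per month. The fourth, the rosiglitazone share among treated persons, is given per period only.

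Switching is described separately. Switching to rosiglitazone is the proportion of patients on other therapies "who switched to rosiglitazone in each of the 4 time periods". Switching away is "the proportion of people, by time period, who switched from rosiglitazone to another anti-diabetic medication", and stopping all antidiabetic drugs is reported with it. A switch counts once two prescriptions for the new therapy have been received.

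The smoothed plots use a four-month window, moved one month at a time and plotted at its midpoint. They cover the four bullet measures only, and the milestones are marked on the graph, "which will clearly display the correspondence between changes in the parameters and the milestone events".

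**The concern.** A proportion of people who switch during a period is a cumulative risk, and it grows with the length of the period even when behaviour does not change. The four periods differ several-fold in length, and the section attaches no person-time or monthly rate to switching or stopping. These period proportions are therefore the only summary over time that is specified for them.

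The first aim in section 2 is to describe utilisation in response to publications, press releases and regulatory decisions. The comparison that matters is before against after a milestone. The first such comparison sets a period of almost seven years against one of eight months. The fourth bullet, the rosiglitazone share, also depends on period length when stated per period only, although it does at least appear in the smoothed plots.

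A lesser issue is the timing shown by those plots. A centred window takes in data from both sides of a milestone, so the curve can begin to move before the event.

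**Working it through.** **1. Period lengths.** The dates come from section 3.6.1. For the end of Period 4, three closing dates are tried: 1 January 2011 (end of the study period, sections 3.1 and 3.3), and the interim and final report dates of 1 April and 1 October 2011 (section 4). Months = days, counting both ends, / 30.4375.

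| Period | Days | Months |
|---|---|---|
| 1 | 2518 | 82.7 |
| 2 | 246 | 8.1 |
| 3 | 972 | 31.9 |
| 4, close 1 Jan 2011 | 101 | 3.3 |
| 4, close 1 Apr 2011 | 191 | 6.3 |
| 4, close 1 Oct 2011 | 374 | 12.3 |

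**2. Raw proportion at an unchanged rate.** Proportion = 1 − (1 − r)^m, for monthly switching probability r and period length m in months. The documents give no rate, so r is assumed. The formula also assumes that everyone is at risk for the whole period.

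| r per month | Period 1 | Period 2 | Period 3 | Period 4 (3.3 / 6.3 / 12.3 months) |
|---|---|---|---|---|
| 0.25% | 18.7% | 2.0% | 7.7% | 0.8 / 1.6 / 3.0% |
| 1% | 56.5% | 7.8% | 27.5% | 3.3 / 6.1 / 11.6% |
| 2% | 81.2% | 15.1% | 47.5% | 6.5 / 11.9 / 22.0% |

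The same formula can be run backwards. If Periods 1 to 3 each showed 10%, the monthly rates behind them would be 0.13%, 1.30% and 0.33%.

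**3. Can a rise look like a fall?** Suppose switching away tripled after May 2007, from 1% to 3% per month (assumed). Period 1 shows 56.5%. Period 2 shows 1 − 0.97^8.08 = 21.8%. The rate has tripled and the reported proportion has more than halved.

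**4. Allowing for turnover.** The cohort is open, and section 3.6.1 itself expects rosiglitazone use to start from zero in 2000. If patients were at risk in Period 1 for 24 to 60 months (assumed), 1% per month gives 1 − 0.99^24 = 21.4% to 1 − 0.99^60 = 45.3%. Period 2 at the same rate, with all 8.1 months at risk, gives 7.8%. Against the tripled rate in Period 2 (21.8%), Period 1 would then show about the same figure at 24 months and about twice that figure at 60. The increase is hidden in the first case and reversed in the second.

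**5. Smoothing windows.** The protocol's own figure reproduces: January to April 2000 has its midpoint at 1 March 2000. By the same rule, its example of first prescriptions in August 2000 falls in the May to August window and is plotted at 1 July 2000, before the month in which they occur.

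For an abrupt fall in prescription counts on 24 May 2007, share shown = post-event days / window days:

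| Plotted at | Window | Share of fall shown |
|---|---|---|
| 1 Apr 2007 | Feb–May | 8/120 = 7% |
| 1 May 2007 | Mar–Jun | 38/122 = 31% |
| 1 Jun 2007 | Apr–Jul | 69/122 = 57% |
| 1 Jul 2007 | May–Aug | 100/123 = 81% |
| 1 Aug 2007 | Jun–Sep | 122/122 = 100% |

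The first two points precede the event.

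Counts of distinct persons behave differently, because someone who stops on 24 May is still counted if an earlier prescription falls in the window. Share of such persons still counted = min(1, pre-event days / refill interval). The window plotted at 1 May has 84 pre-event days, so at assumed refills of 28, 56 or 84 days all are still counted, and at 90 days 93% are. The window plotted at 1 June has 53 pre-event days, so the shares are 100%, 95%, 63% and 59%. For persons, the fall may therefore appear late.

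**The case against.** The strongest reply is that the section promises evaluation by calendar month as well as by period, that the counts are given per month, and that period dates are stated, so an attentive reader could allow for length. That holds for the first three bullets. It does not hold for switching, because the sentences that define those measures name periods only and the plots exclude them. Nor is this detail left for a later plan: section 3.6 is headed as the analysis plan and fixes the measure.

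The percentages in the second table are illustrations. They assume a closed cohort and a chosen rate, and turnover reduces the contrast, as step 4 shows. That objection stands as to size, not direction.

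Several stronger readings are tempting, and the documents do not support them:

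- **A 17-fold spurious difference between Periods 1 and 4.** This is 56.5% / 3.3%. It needs 1% per month, full-period risk and a close on 1 January 2011, whereas the section leaves the closing date open.
- **Only switches in the first 10 to 16 days after the suspension can be confirmed.** This needs the same close and a refill interval of 84 to 90 days, which the documents do not give. With 28-day refills, 100 − 28 = 72 days would qualify.
- **Switching away would seem to fall after the suspension merely because Period 4 is short.** This supposes an unchanged rate once the drug is suspended, when stopping would be expected to surge.
- **All the smoothed curves would place the fall before the press release.** This is certain only for prescription counts.
- **The spline is wrong because it is continuous.** The "regression splines, with knots (nodes) at the milestone dates" are an expectation for optional models whose form is left to be chosen as appropriate. Nothing rules out a level change.

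**Conclusion.** The point holds for switching to rosiglitazone, switching from it and stopping. As specified, these proportions mix behaviour with period length. The clearest case is Period 1 against Period 2, where the lengths differ by 82.7 / 8.1, about tenfold, and both dates are fixed in the protocol. An unchanged 1% per month would read as 56% and then 8% with full-period risk, or as 21% to 45% and then 8% if time at risk in Period 1 were 24 to 60 months. The distortion disappears only if time at risk in Period 1 were as short as in Period 2. A true increase after the May 2007 warning could be hidden or reversed. The size depends on assumed rates and turnover; the direction does not.

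Period 4 adds uncertainty because its length ranges from 3.3 to 12.3 months on the closing dates tried, and the two-prescription rule loses switches made close to whichever date applies. How many are lost cannot be computed from the documents.

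The smoothing point is secondary. Up to 31% of an abrupt fall in prescription counts is drawn before the May 2007 event, while person-based measures may lag, so the smoothed curve alone should not be used to time a change.

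**What to change.** - Report switching to rosiglitazone, switching from it and stopping as rates per 1,000 person-months on the originating therapy, by period and by calendar month.
- Give the fourth bullet, the rosiglitazone share, per month as well as per period.
- Apply the same two-prescription rule in every period, and date the switch at the first prescription of the new therapy. Relaxing the rule for Period 4 alone would make that period non-comparable.
- State the data closing date, and say how switches too late to be confirmed by it are handled.
- Plot the unsmoothed monthly values, already planned for the first three bullets, with the milestones marked, beside the smoothed curve. Do not time changes from the smoothed curve alone. Restarting the windows at each milestone is not advised, because it would impose the breaks that the section deliberately avoids at this stage.

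The cost is wording and programming on data already to be held. Time on therapy needs a rule for how long a prescription covers a patient, but identifying stopping already requires one. Monthly points will be noisier in Denmark, with about 2,400 rosiglitazone users, which is a reason to keep the smoothed curve alongside.
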